#### 9.2.1.2 Requirement for Renal Replacement Therapy (RRT)

The hypotheses of interest relating to RRT are as follows:

$$H_0: P_t = P_c$$

$$H_1: P_t \neq P_c$$

where  $P_t$  and  $P_c$  represent the proportion of subjects requiring RRT in the treatment and control groups, respectively. Treatments will be compared using the chi-square test. Subjects that enter the study on dialysis, or are on chronic dialysis, are excluded from this endpoint. Summary of this endpoint will include the number and percentage of patients requiring RRT, a 95% confidence interval for the risk difference in the two arm percentages calculated using the normal

approximation to the binomial distribution, and the p-value from the test described above. If the observed event rates are less than 10% in either treatment group, a Fisher's exact test will be used to compare treatments instead of the chi-square test, and the 95% confidence of the risk difference will be based on the Wilson method instead of the normal approximation to the binomial distribution.

### 9.2.1.3 Requirement for Ventilator Use

The hypotheses of interest relating to ventilator use are as follows:

$$H_0: P_t = P_c$$

$$H_1: P_t \neq P_c$$

where  $P_t$  and  $P_c$  represent the proportion of subjects requiring ventilator use in the treatment and control groups, respectively. Treatments will be compared using the chi-square test. Subjects that enter the study on ventilation are excluded from this endpoint analysis. Summary of this endpoint will include the number and percentage of patients requiring ventilator use, a 95% confidence interval for the risk difference in the two arm percentages calculated using the normal approximation to the binomial distribution, and the p-value from the test described above. If the observed event rates are less than 10% in either treatment group, a Fisher's exact test will be used to compare treatments instead of the chi-square test, and the 95% confidence of the risk difference will be based on the Wilson method instead of the normal approximation to the binomial distribution.

### 9.2.1.4 Length of ICU Stay

The distribution of treatments with respect to length of ICU stay (days) will be compared between treatments using the Wilcoxon Rank Sum test given the expected skewness in this variable. Subjects that die while in the ICU will be censored from the analysis. ICU length of stay will be calculated using the earliest of date that the subject is medically ready for discharge when captured, the date of discharge, or the study exit date.

Summary of this endpoint will include the mean, median, quartiles, minimum, maximum and standard deviation of days for each treatment arm, a 95% confidence interval for the difference in the two treatment arm mean days, and the p-value from Wilcoxon Rank Sum test.

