7.3.2 Secondary Endpoints

Secondary endpoints to be evaluated:

1. Length of ICU stay (days) until subject is medically ready for discharge
2. Number of hours free from ventilator use
3. Requirement for mechanical ventilation
- 4.
5. Number of hours free from vasopressor use
6. Changes in serum creatinine levels from baseline
7. Requirement for renal replacement therapy (RRT)
8. Mean volume of fluid between the two treatment groups
9. Incidence of Major Adverse Cardiac Event (MACE)
10. Incidence of Adverse Events (AE)
11. Number of ICU readmissions
12. 30 day in-hospital Mortality rate
13. Discharge location
14. Mean difference in fluid balance at ICU discharge

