12.4 Secondary and Exploratory Endpoints

Secondary objectives that have been pre-specified to be included in the formal statistical analysis will be tested in sequential fashion using the Holms step-down procedure for type-I error rate correction if and only if the primary objective passes according to the criteria outlined above. At the conclusion of the trial, the key secondary endpoints will be ordered sequentially from most significant to least significant. The endpoints will then be tested in order at adjusted levels of significance (i.e. E1: 0.05/k, E2: 0.05/k-1; E3: 0.05/k-2, where k=number of specified endpoints). Once an endpoint fails, all following endpoints will not be tested. Following is a list of key secondary endpoints:

Following is a list of key secondary endpoints for formal testing:

- Length of ICU stay (days) until subject is medically ready for discharge
- Number of days free from ventilator use (30 day period)
- Requirement for mechanical ventilation
- Number of days free from vasopressor use
- Changes in serum creatinine levels from baseline
- Requirement for renal replacement therapy (RRT)

Additional secondary endpoint have also been identified for testing, but will not be included in the formal statistical testing procedures for key secondary endpoints:

- Incidence of Adverse Events (AE)

- Number of ICU readmissions
- Mortality rate
- Mean volume of treatment fluid
- Incidence of Major Adverse Cardiac Event (MACE)
- Discharge location
- Mean difference in fluid balance at ICU discharge

Additional sub-analyses have been planned for the primary and key secondary endpoints. Primary and secondary endpoints will also be evaluated by the following subgroup analysis:

- Patient disease state
- Patients determined to be fluid responsive vs non-fluid responsive
- AKI measures in patients determined to increase serum creatinine levels from baseline vs decrease serum creatinine levels from baseline
- Enrollment time frame

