#### 4.2.2 SECONDARY ENDPOINTS

##### 4.2.2.1 For formal testing

Key secondary endpoints for the purposes of formal statistical testing are:

- Changes in serum creatinine level from baseline to 72 hours (key secondary endpoint)
- Requirement for renal replacement therapy (RRT)
- Requirement for ventilator use
- Length of ICU stay (days) until subject is medically ready for discharge
- Number of hours with ventilator use (30-day period)
- Number of hours with vasopressor use

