### 9.2.1.5 Number of Hours with Ventilator Use

The hypotheses of interest relating to the number of hours free from ventilator use (within 30 days) are as follows:

$$H_0: \mu_t = \mu_c$$

$$H_1: \mu_t \neq \mu_c$$

where  $\mu_t$  and  $\mu_c$  represent the mean number of hours in the treatment and control groups, respectively. The treatment groups will be compared with respect to the mean hours using a two-

sided two-sample t-test. Subjects that enter the study on ventilation are excluded from this endpoint analysis. Summary of this endpoint will include the mean, quartiles, median, minimum, maximum and standard deviation of hours for each treatment arm, a 95% confidence interval for the difference in the two treatment arm mean hours, and the p-value from the test described above.

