#### 9.2.1.6 Number of Hours with Vasopressor Use

The hypotheses of interest relating to the number of hours with vasopressor use are as follows:

$$H_0: \mu_t = \mu_c$$

$$H_1: \mu_t \neq \mu_c$$

where  $\mu_t$  and  $\mu_c$  represent the mean number of hours in the ICU in the treatment and control groups, respectively. The treatment groups will be compared with respect to the mean hours using a two-sided two-sample t-test. Summary of this endpoint will include the mean, median, quartiles, minimum, maximum and standard deviation of hours for each treatment arm, a 95% confidence interval for the difference in the two treatment arm mean hours, and the p-value from the test described above.

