#### 9.2.2.3 Mortality Rate

The mortality rate will be summarized by treatment arm in a table. The summary will include the number and percent of subjects who died by arm; Kaplan-Meier mortality curves will be presented for each treatment group. Though no formal hypothesis tests are planned, 95% confidence intervals for the difference in rates between the two arms will be completed and included using the normal approximation to the binomial distribution or Wilson method (if an observed rate is less than 10% in any treatment group).

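### The formal ICU-stay test appears to drop ICU deaths and so compares ICU survivors only, and the ventilator-hours endpoint names two different variables with no rule for deaths

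*SAP*

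**What the plan says.** **ICU stay.** SAP 9.2.1.4 says the arms "will be compared between treatments using the Wilcoxon Rank Sum test given the expected skewness in this variable". It then says "Subjects that die while in the ICU will be censored from the analysis". No censored-data or competing-risk method is named, and no rank or value is given to a death. Stay ends at the earliest of medical readiness, discharge or study exit; death is not listed. SAP 7.5 places the endpoint in the formal sequence at two-sided 0.05.

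**Ventilator hours.** SAP 9.2.1.5 is headed hours *with* ventilator use, as are the endpoint lists in SAP 2, 4.2.2.1 and 7.5. Its hypothesis sentence reads "The hypotheses of interest relating to the number of hours free from ventilator use (within 30 days) are as follows". Protocol 7.3.2 has "Number of hours free from ventilator use", and Protocol 12.4 has *days* free over 30 days. The only exclusion in 9.2.1.5 is ventilation at entry. SAP 7.3 lists death as a cause of missing data and says missing data are not imputed, but it does not define ventilator hours for a subject who dies.

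**Vasopressor hours.** In SAP 9.2.1.6 the means "represent the mean number of hours in the ICU in the treatment and control groups, respectively", which is a different quantity from the one in the heading. No time window is given.

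**Mortality.** SAP 9.2.2.3 gives counts, Kaplan-Meier curves and an interval: "Though no formal hypothesis tests are planned, 95% confidence intervals for the difference in rates between the two arms will be completed".

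**The concern.** A rank-sum test needs one complete value per subject. If ICU deaths are taken out, subjects leave the comparison because of something that happened after randomisation. Where sicker patients both stay longer and die more often, the arm with more deaths loses more of its long stayers, and its survivors look quicker to recover. Some ICU deaths must be expected in sepsis with refractory hypotension. A formal statement that Starling shortens ICU stay could then rest on survivors only, with no formal mortality test beside it.

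For ventilator hours, two programmers could follow SAP 9.2.1.5 and analyse different variables. The two agree only when every subject contributes the full window, which a death prevents. An undefined choice of this kind should not be left until results are known.

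**Working it through.** The documents give no mortality rate, and no effect size or power for ICU stay or ventilator hours, so there is no figure of the plan's own to reproduce. What follows is reading plus an illustration on assumed inputs.

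**1. What can "Subjects that die while in the ICU will be censored from the analysis" mean?** There are two readings.
- *Deaths dropped.* This is the natural one, since the test named has no place for a censored value. At assumed mortality of 15% control and 30% Starling, 40 × 0.15 = 6 and 80 × 0.30 = 24 subjects leave, so 34 + 56 = 90 of 120 remain.
- *Stay ends at death, treated as study exit.* An early death then counts as a short, favourable stay. With an assumed median death time of 2 days, independent of stay, 15% v 30% mortality favours Starling in 10.7% of trials.

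Neither reading is sound.

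**2. Size under the first reading.** Taken from the SAP: 80:40, rank-sum test, two-sided 0.05. Assumed: stay = 4·exp(0.8z) days with z standard normal (median 4 days), the same in both arms, so there is no true effect. A subject dies if ρz + √(1−ρ²)·e exceeds the arm's mortality quantile. Deaths are dropped; 10,000 trials per cell. Share of trials significantly favouring Starling (nominal 2.5%):

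| Mortality, control v Starling | ρ = 0 | ρ = 0.3 | ρ = 0.6 |
|---|---|---|---|
| 20% v 20% | 2.7% | 2.7% | 2.3% |
| 20% v 25% | 2.7% | 3.0% | 4.0% |
| 20% v 30% | 2.5% | 3.7% | 6.3% |
| 15% v 30% | 2.4% | 4.7% | 9.4% |
| 30% v 15% | 2.9% | 1.2% | 0.3% |

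The first row and the first column show no inflation. The last row shows the rule working against Starling: control is favoured in 2.4%, 4.4% and 9.0% of trials. The mechanism is visible in the medians: at ρ = 0.6 the survivors' median stay is 3.54 days at 15% mortality and 3.18 days at 30%, although the underlying stay is the same.

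**3. Which analysis set these rates describe.** They assume that ICU discharge ends the monitoring requirement, as in the mITT wording (SAP 6.3). The PP wording (SAP 6.4) requires 72 hours of monitoring in the Starling arm and does not mention discharge. Read literally, it also removes Starling survivors who leave before 72 hours. In the cells run (20% v 20% and 15% v 30%), the same simulation then favours Starling in 0.0% of trials and control in 73–88%. That comes from the PP definition and is a separate matter.

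**4. Ventilator variable.** Over 720 h (30 × 24), hours free = 720 − hours with, for anyone observed throughout, so the t-test p-value is identical. Now take a subject ventilated for 100 h who dies at hour 100. Hours with = 100, the same as a survivor ventilated for 100 h. Hours free = 620 if time after death counts as free, and 0 if it does not. The survivor has 620. SAP 9.2.1.5 does not say which applies.

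**5. Behaviour of the remedy.** With deaths given the worst rank in all randomised subjects (80:40), each arm is favoured in 2.2–2.5% of trials at 20% v 20%, so the level holds. The analysis set matters. If Starling deaths before 72 hours are removed and control deaths kept, then at equal 20% mortality Starling is favoured in 18.3–19.5% of trials (assumed median death time 48 h) or 7.1–7.4% (120 h).

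**The case against.** The strongest reply is that the SAP states a rule, if loosely: deaths are excluded, mortality is shown alongside, and a reader can see any imbalance. Worst ranking answers a different question and can produce a shorter-stay result from mortality alone. It is true that this is partly a choice of estimand. But 9.2.1.4 does not present its test as a comparison among survivors, and the word it uses does not fit the test it names.

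A second reply is that the size is modest. At 20% v 25% mortality the rate is 2.7–4.0%; the 9% figure needs a doubling of mortality on Starling and a correlation of 0.6, neither of which comes from the documents. A formal claim also requires the primary endpoint and the earlier secondaries to succeed. The list in SAP 7.5 puts ICU stay fourth, though its narrative treats it as second. All of this stands.

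A third reply is that the with/free conflict is mostly editorial, since one SAP sentence keeps the protocol's wording. That is fair while everyone is followed for the full window, but not once subjects die.

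A reader might go further and infer that the plan is tilted towards the device, or that these percentages are the false-claim rate of the formal test. The documents support neither. They give no mortality rate, the direction depends on which arm has more deaths, and the SAP's primary set is PP, for which the rates above do not hold on a literal reading. Nor is bias shown for vasopressor hours, whose direction is consistent throughout SAP 9.2.1.6.

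**Conclusion.** The point holds as a defect in the definition of formally tested secondary endpoints. It should be fixed, but it does not threaten the primary analysis.

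- **ICU stay:** on the natural reading, ICU deaths are dropped and the test compares ICU survivors. (Subjects who die after leaving the ICU stay in.) There is no inflation if mortality is equal or death is unrelated to stay. Otherwise the test can favour the arm with more deaths: about 2.5%, 5% and 9% of trials favour Starling at 15% v 30% mortality for correlations of 0, 0.3 and 0.6, with the reverse if Starling mortality is lower. These figures rest wholly on assumed inputs, at 80:40, outside the literal PP set. They describe the ICU-stay test alone, and formal claim rates are lower.
- **Ventilator hours:** SAP 9.2.1.5 contradicts itself on the variable, disagrees with the protocol, and has no rule for deaths. This follows from the text and needs no assumption.
- **Vasopressor hours:** a wording correction only.

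**What to change.** 1. **SAP 9.2.1.4.** Replace the sentence on censoring with a rule that keeps deaths in the test: Wilcoxon rank-sum, ICU deaths given the worst rank. Run it in all randomised subjects, or in mITT with deaths before 72 hours kept in both arms, and state that this is the set for the formal ICU-stay test. Do not apply it in the PP set, which requires 72 hours of monitoring in the Starling arm only. Report survivors-only stay as a descriptive summary beside mortality.
2. **SAP 9.2.1.5.** Use one variable and one unit in the heading, the hypothesis and SAP 2, 4.2.2.1 and 7.5, with a stated death rule. One option is hours alive and ventilator-free, deaths set to zero, compared by Wilcoxon. The window must be one that the collected follow-up covers: the protocol synopsis collects outcomes to hospital discharge, while SAP 3.2 refers to 30-day follow-up.
3. **SAP 9.2.1.6.** Correct the definition of the means and state the window.

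**Cost.** Items 1 and 3 need no new data. Item 1 is more than a wording change, however: SAP 9 makes PP primary for all efficacy analyses, so an exception has to be written in for this endpoint. Item 2 needs a check of follow-up; if vital status after discharge is not collected, use a shorter window or state the assumption made.

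**Downside to state in the SAP.** Both endpoints become composites with mortality. With no effect on stay or ventilation, at 15% v 30% mortality the worst-rank ICU-stay test favours the lower-mortality arm in about 14–28% of trials, and the deaths-as-zero ventilator test in about 27–31% (assumed: 720 h window, death independent of ventilation). A significant result must therefore be read beside the mortality figures and the survivors-only summary.

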## 5 SAMPLE SIZE

Subjects will be randomly assigned in a 2:1 ratio to treatment with Starling SV or to treatment with standard of care, stratified by time window of enrollment (0-6 hours, 6-12 hours, and 12-24 hours). The primary effectiveness endpoint for this study is fluid balance at ICU discharge.

Minimum enrollment ( $N_{\min}$ ) in the study will be set at 120 subjects (80 Starling SV and 40 control) to power at 80% for demonstration of superiority of means for the secondary endpoint of creatinine levels as a measurement of change from baseline at 72 hours. The secondary endpoint for change in creatinine levels at 120 evaluable subjects displays 80% power at a two-sided alpha level of 0.05 to demonstrate superiority of Starling SV under an assumption of an average treatment effect of -1.4 mg/dL with a standard deviation of 2.5 mg/dL.

Under an assumption of an average treatment effect of -2 L with a standard deviation of 3 L, the sample size of 120 evaluable subjects provides 92.7% power in a test of superiority of means for the primary effectiveness endpoint at a two-sided 0.05 level of significance.

The trial will incorporate a sample size re-estimation (SSR) at the time of the interim look (after 90 patients have been evaluated for the key secondary endpoint) based on promise for superiority in the key secondary endpoint. Sample size re-estimation, described in further detail in Section 3.1, will result in a maximum of 210 total evaluable subjects, or no more than 1.75 times the minimum of 120.

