### 7.5 MULTIPLE COMPARISONS AND MULTIPLICITY

It is recognized that with a multiplicity of tests comes inflation in the chance of a false finding. Therefore, formal statistical testing will only be done for the following secondary endpoints:

- Changes in serum creatinine level from baseline to 72 hours (key secondary endpoint)
- Requirement for renal replacement therapy (RRT)
- Requirement for ventilator use
- Length of ICU stay (days) until subject is medically ready for discharge
- Number of hours with ventilator use (30-day period)
- Number of hours with vasopressor use

These endpoints will be tested in a hierarchical (sequential) manner in the order given above (and testing will only proceed if a significant beneficial treatment effect is detected in the primary endpoint). Specifically, the first secondary endpoint (change in creatinine) will be compared between treatments at a two-sided 0.05 level of significance. If significant in the direction favoring Starling SV, then Starling SV will be considered beneficial on change in serum creatinine level, and the next endpoint (ICU stay) will be compared between treatments at a two-sided 0.05 level of significance; otherwise the statistical testing will stop and Starling SV will not be considered statistically significantly beneficial on any secondary endpoint. If the treatment comparison is able to proceed to this next secondary endpoint of ICU stay, it will be carried out at the two-sided 0.05 level of significance. If the treatment comparison is significant in the direction favoring Starling SV, then Starling SV will be considered beneficial on this endpoint and testing will proceed in a similar manner for the remaining endpoints; otherwise, treatment comparisons will stop and Starling SV will not be considered beneficial on this second secondary endpoint of ICU stay nor on all endpoints after it in the above sequence.

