#### 9.2.2.2 Number of ICU Readmissions

The number of ICU readmissions through 30 days will be summarized by treatment arm in a table. The summary will include the number and percent of subjects with 0, 1, or >1 ICU readmissions. Though no formal hypothesis tests are planned, 95% confidence intervals for the difference in rates between the two arms will be completed and included using the normal approximation to the binomial distribution or Wilson method (if an observed rate is less than 10% in any treatment group).

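### The formally tested ICU stay ends at the medically-ready date for some subjects and at discharge for others, depending on what was recorded

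*SAP*

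**What the plan says.** Protocol 7.3.2 names the endpoint "Length of ICU stay (days) until subject is medically ready for discharge". Protocol 12.4 and SAP 4.2.2.1 and 7.5 use the same name. None of them limits it to subjects whose readiness happened to be documented.

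SAP 9.2.1.4 gives the derivation: "ICU length of stay will be calculated using the earliest of date that the subject is medically ready for discharge when captured", followed by "the date of discharge, or the study exit date". It does not say whether discharge means leaving the ICU or leaving the hospital. The analysis is a "Wilcoxon Rank Sum test given the expected skewness in this variable". On deaths it says "Subjects that die while in the ICU will be censored from the analysis".

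SAP 7.5 places ICU stay in the formal sequence, where "it will be carried out at the two-sided 0.05 level of significance". SAP 9.2.2.2 handles readmission separately: "The number of ICU readmissions through 30 days will be summarized by treatment arm in a table". Readmissions do not lengthen the stay.

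Neither document defines medical readiness, names who judges it, or says what happens to a ready date if the patient worsens before leaving. No analysis of this endpoint on a single end date for all subjects is planned. The missing-data sensitivity analysis in SAP 7.3 covers the primary endpoint only.

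**The concern.** The end of the stay should be the same event for everyone. Here the paperwork helps to decide which event is used. A subject with a recorded ready date stops accruing days at readiness. An otherwise identical subject without one goes on accruing days until departure, including any wait for a bed or transfer.

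The endpoint is tested at two-sided 0.05 and later endpoints depend on it. Two follow it in the list in SAP 7.5, or four if one follows the narrative there, which treats ICU stay as second in line. Treatment is guided at the bedside and no blinding is described, so staff who know the arm may judge and record readiness. If they recorded it more often in one arm, that arm's stays would look shorter with no real effect, and nothing in the planned output would show it.

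The unstated reversal rule is a second gap. If an early ready date is kept after the patient deteriorates, a long stay is scored as a short one.

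**Working it through.** **No figure to reproduce.** The documents give no effect size, SD or power for ICU stay. The check is a reading of the rule, followed by an illustration of its consequence.

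**1. The rule.** Let R be the ready day, D the discharge day and E the study exit day. The score is min(R, D, E) if R was recorded and min(D, E) if it was not.

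**2. The rule applied** (days are assumed; E is not earlier than D):

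| Subject | R | R recorded? | D | Score |
|---|---|---|---|---|
| A | 3 | yes | 5 | min(3, 5) = 3 |
| B | 3 | no | 5 | 5 |
| C | 3, then deteriorates; day 3 kept on the form | yes | 12 | min(3, 12) = 3 |

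A and B had the same stay and score 2 days apart. This needs no assumption beyond incomplete recording and a gap of at least one counted day between readiness and departure. C arises only if the form keeps the day-3 date.

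**3. Expected shift with no true difference.** A subject without a ready date carries the extra delay from readiness to discharge. With capture proportions p_T and p_C and the same mean delay L in both arms:

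shift in mean (control minus treatment) = (p_T − p_C) × L

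- Equal capture: 0 × L = 0 days.
- 90% vs 60%, L = 0.5 day: 0.30 × 0.5 = 0.15 day.
- 90% vs 60%, L = 1 day: 0.30 × 1 = 0.30 day.

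**4. Effect on the test.** The arm sizes come from SAP 5, where minimum enrolment "will be set at 120 subjects (80 Starling SV and 40 control"). Everything else is assumed: lognormal time to readiness (median 3 days with CV 1, or median 4 days with CV 0.8), exponential delay, whole days, no true effect, 4,000 simulated trials per setting, two-sided Wilcoxon at 0.05.

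| Capture, treatment vs control | Mean delay | Type I error |
|---|---|---|
| 90% vs 90% | 0.5–1 day | 4.6–5.0% |
| 90% vs 60% | 0.5 day | 5.7–6.1% |
| 90% vs 60% | 1 day | 8.7–9.3% |

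The simulated mean shift at 90% vs 60% is 0.14 to 0.33 day, in line with step 3. The Monte Carlo standard error near 5% is √(0.05 × 0.95 / 4000) = 0.34 percentage points, so the 0.5-day rows are only modestly above nominal.

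A second set of assumptions (median 3 days, log-SD 0.7, mean delay 0.5 to 2 days) shows the same pattern. Equal 60% capture gives 4.6–5.1% at 80:40. Capture of 70% vs 50% gives 5.8–12.0% at 80:40 and 6.4–16.0% at 140:70, the split at the maximum of 210. A fixed bias does more harm in a larger trial.

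**5. Setting unrecorded ready dates to missing.** SAP 7.3 does not impute missing data for secondary endpoints, so those subjects would drop out. At 90% vs 60%, 80:40 becomes 72:24. The information measure n₁n₂/(n₁+n₂) falls from 80 × 40 / 120 = 26.7 to 72 × 24 / 96 = 18.0, a loss of 1 − 18.0/26.7 = 33%.

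**The case against.** The case for leaving the rule alone has real substance.

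- **Unequal capture is assumed.** Both arms share sites, forms and monitoring. With equal capture the test keeps its level, and an imbalance could equally run against the device. This stands: the error rates above are illustrations. They are also conditional on reaching the test, because the primary and at least creatinine must succeed first.
- **The fallback is sensible.** Discharge is an upper bound on readiness and keeps every survivor in the analysis. This also stands, and it is why unrecorded ready dates should not be set to missing.
- **Capture may be nearly complete.** A reader might infer that capture must be poor because the ready date is absent from Protocol 9.3.3 and Table 1. The documents do not support that: ICU admission and discharge dates, RRT and discharge location are absent there too, although endpoints need them. The SAP's own proviso about capture shows that gaps were foreseen, but not how many.
- **Reversal.** A reader might infer that the SAP takes the first of several ready dates. In its text, earliest ranges over readiness, discharge and study exit, not over repeated ready dates, and a form with one overwritten field would avoid the problem. Nor does scoring subject C at day 3 contradict the protocol, which has no reversal rule. The point is undefined, not wrong. Ventilator and vasopressor hours and mortality might show a serious relapse, but they do not correct the stay.

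None of this removes the mixed end point or supplies an analysis that would expose an imbalance.

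**Conclusion.** The point holds as a defect of definition with a possible, unquantified bias. The formally tested variable ends at different events for different subjects, and documentation alone can separate identical stays. With equal capture the cost is noise and an unclear estimand, with error about 5%. With unequal capture the comparison is biased by roughly the difference in capture times the mean delay. At an assumed 90% vs 60% and 0.5 to 1 day, that is about 0.15 to 0.30 day and a type I error of 5.7% to 9.3%. Capture rates, delay and stay distribution are all assumptions.

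A reader might go further and conclude that the ICU-stay result will be biased towards the device. The documents do not support that, because they say nothing about capture by arm. The rule after a reversal is an omission to be filled. The change should be made before database lock, so that nobody chooses between two definitions of stay after seeing results.

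**What to change.** 1. Make the ready date a required eCRF item for every subject who leaves the ICU alive, and retrieve it from the chart where it is absent.
2. State in SAP 9.2.1.4 which ready date counts when a patient is declared ready and then deteriorates before leaving, and that discharge there means ICU discharge. Add a definition of readiness and who assesses it.
3. Keep ICU discharge as the fallback where the ready date cannot be retrieved. Do not set such subjects to missing.
4. Report the proportion with a recorded ready date by arm.
5. Pre-specify a sensitivity analysis that repeats the Wilcoxon test with the actual ICU discharge date for all subjects.

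The cost is a few lines of SAP text, one form field, some retrospective chart review and one extra table. Protocol 7.4 expected enrolment to end in Q2 2018 and the forms reviewed for the SAP date from December 2017, so much of the capture may have to be retrospective. That makes items 4 and 5 the essential protection.
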